4.1 OVERALL DESIGN

This is an observational cohort study of CASH cases with no intervention. Seven high-volume cavernous angioma sites have been identified for this project. We propose to activate sites and prepare data structure in year 1, then prospectively screen and enroll 200 CASH cases in years 2-5 at multiple sites. We shall collect harmonized baseline data, and enroll a subset of approximately 120 cases into the follow-up and imaging biomarker validation (FUBV) arm at 4 or so sites to assess and compare clinical outcomes, biomarker outcomes, and functional status and patient-reported quality of life outcomes for potential use in future clinical trials.

Clinical Coordinating Center (CCC):

The Clinical Coordinating Center, located at the University of Chicago, will train site coordinators on the protocol and data entry, as well as track enrollment rates. The CCC will also be responsible for answering site questions about enrollment and subject eligibility.

Data Coordinating Center (DCC):

The Data Coordinating Center, located at Johns Hopkins University, will develop and oversee the trial electronic data system to ensure the integrity of data collection, safety and coordination of data storage and access. Study site staff will be trained, sites activated and pilot cases completed in year 1 and data collection thereafter for years 2-5. The DCC shall perform data monitoring and generate data reports for analysis by Investigators as proposed in the respective Specific Aims 1-3. The DCC will review the online case forms for completeness, logic, and consistency, then verify the entered data against the uploaded source records/data collection worksheets in a random 5% sample of cases. Routine queries identified in this process will be entered into the EDC system (triggering an automated notice to the site). The monitors will then work with the site personnel to obtain correction of all data errors and resolution of the corresponding queries.

4.2 SCIENTIFIC RATIONALE FOR STUDY DESIGN

Justification of Rare Disease. Brain CA lesion prevalence has been estimated at 0.46-0.63% of the population based on consecutive imaging studies in the MRI era²⁷⁻²⁹. A 0.5% lesion prevalence was confirmed by the detection of 131 CAs among 24,535 consecutive autopsies³⁰. In these consecutive imaging or autopsy studies, consistently <10% of lesions had manifested a SH. In the one prospective population based study in the MRI era, 12% of detected CAs presented with a SH¹⁹. Based on <10-12% CASH prevalence among all cavernomas and assuming 0.5% of 325 million adults of the U.S. population harbor a CA, it is projected that fewer than 162,500 to 195,000 adults are living with a cavernoma that has bled at least once. Fewer numbers would harbor a CA with a more recent SH, warranting therapeutic targeting. Based on an estimated prevalence of 60,000 cavernomas in the U.S. with clinical symptoms warranting therapeutic intervention, Recursion Pharmaceuticals received Orphan Drug Designation in 2010 from the U.S. Food and Drug Administration (FDA) (<http://www.pr.com/press-release/640210>).

Similarly, the European Consortium Orphanet has designated brain CA as a rare disease, Orpha164 (http://www.orpha.net/consor/cgi-bin/OC_Exp.php?lng=EN&Expert=164).

Knowledge Gaps Regarding the Prevalence of CASH and Baseline Characteristics. For planning and executing multi-site clinical trials, it is unclear what fraction of CA patients would meet the likely trial eligibility criteria of SH within the prior year with an unresected lesion. That prevalence varied between 10-25% in the three largest ongoing CA research databases at U.S. institutions, with different referral patterns and enrollment criteria. This might vary further at other institutions, and with systematic screening. **Prospective prevalence of CASH in systematic screening of CAs, and enrollment rates at multiple sites are not known.** These data are essential for the proper design of clinical trials, including the number of prospective sites needed. It is further unclear how CASH cases might vary by age, sex, familial versus sporadic, lesion size and location, associated venous anomaly, past bleeds, and baseline disability. These features varied or were not assessed consistently in the 3 active prospective CA research databases in the U.S. More importantly, the **assessment of these features at multiple sites has never been harmonized or adjudicated. Further, it is unclear what functional status and Quality of Life (QoL) instruments best capture the clinical impact of CASH.** Inclusion/exclusion criteria and stratification for these characteristics will be important in clinical trials, as they will impact natural risk, and potentially the effect of putative therapies. These critical knowledge gaps will be addressed in Specific Aim 1 of this proposal.

Opportunities and Challenges with Novel Biomarkers Linked to Clinical Bleeding in CAs.

Vascular leak is a fundamental feature of CAs, mediating hemorrhage and the associated accumulation of non-heme iron (including hemosiderin). Pre-clinical studies demonstrated rescue of vascular permeability and decreased lesional iron deposition with ROCK inhibitors and statins³¹, and B-cell depletion therapy³² in murine CA models recapitulating the human disease. [name]'s group in Chicago implemented a novel MRI application of assessing iron deposition in human CAs using quantitative susceptibility mapping (QSM)³³⁻³⁶. Mean lesional QSM was shown to reflect actual iron concentrations assessed by mass spectroscopy in resected human CA specimens³⁵. Researchers in Chicago and New Mexico optimized a second technique, dynamic contrast enhanced quantitative perfusion (DCEQP) measure on MRI in human subjects, reflecting mechanistically postulated vascular hyper-permeability^{33, 34, 37-39}. The [name] team used both QSM and DCEQP successfully in over 200 CA subjects and showed strong inter-observer agreement in QSM and DCEQP measurements, stability of both measurements in clinically stable lesions, and reproducibility across MRI instrument platforms at the Chicago site^{36, 38}. As predicted by the conservation of mass hypothesis, CA lesions with greater permeability (K_i) had higher lesional iron content (QSM)³⁶, and lesional iron content was greater in older patients and in CAs with prior SH³⁶. More recent studies demonstrated a significant increase of mean lesional QSM and DCEQP K_i in human CA lesions manifesting interval SH or growth during longitudinal follow-up, while these did not change in stable lesions³³. There were tight, sensitive and specific thresholds of QSM and DCEQP increases in association with clinical events³³. Therefore, it is postulated that the QSM and DCEQP may be used as *in vivo* measures of hemorrhagic activity and vascular leak, respectively, and may reflect sensitive, clinically meaningful therapeutic effect in human CAs. No other biomarkers have been as linked mechanistically to CA, nor associated as closely with clinical events.

However, the QSM validations and clinical correlations in CAs have been conducted at a single site to date, and DCEQP was applied to CAs at only two sites using slightly different protocols. FDA approved image acquisition sequences of QSM and DCEQP have been implemented on different MRI instruments from major manufacturers, but their validation at multiple sites have not been reported, nor specifically in CAs. The feasibility, accuracy, precision and reproducibility of biomarker measurements at multiple sites are critical to their potential application as outcomes instruments in clinical trials. We propose a rigorous approach to address these gaps in Specific Aim 2 of this project.

Knowledge Gaps Regarding Follow- and

Outcomes Assessment. Reducing the rate of recurrent SH as a clinical outcome would decrease the burden of disease, since a single SH can lead to devastating neurologic sequelae. This would be an approvable outcome, adjudicated, readily defined and easy to measure. Yet there are many knowledge gaps and potential obstacles to planning clinical trials based on this primary outcome. Attempting to power a study

Table. Power Calculation Models

Numbers of patients needed, based on different re-bleed rates. Calculated by Parexel, 90% power, 1-sided, Type 1 error 0.025, treatment allocation 1:1, dropout rate 10%.

Annual rate of SH in control	Follow-up period	Reduction in SH rate (%)	Sample size/group
6%	1.5 yrs	25%	3341
	1.5 yrs	50%	720
15%	1.5 yrs	25%	1161
	1.5 yrs	50%	253
30%	1.5 yrs	25%	435
	1.5 yrs	50%	98

based on recurrent SH would require at least a 1- to 2-year study and a significant number of patients (Table). The relative mix of lesions with different re-bleed rates will greatly influence the sample size needed to show treatment effect based on this primary outcome. Limiting trials to brainstem lesions would enhance statistical power, but also restrict recruitment and prevent generalizability of a drug's effects to other CASH cases that could benefit. Other studies suggest an equally high rate of SH in deep supra-tentorial and possibly cerebellar CAs²¹. **The rates of recurrent SH have never been assessed prospectively at multiple sites in CASH trial candidates.**

Moderate to severe disability after SH has been reported in 11-22% of patients^{17, 40-42}. A CA re-bleed causes significantly greater disability than initial SH²². The proportion of CASH cases with any functional disability varied between 26 and 65% at U Chicago, Mayo and BVMC cohorts. Only two studies assessed QOL in CAs, and both were limited to surgical patients. One study⁴³ used Karnofsky performance scale, Patzold Rating and SF-36, and the second⁴⁴ used only SF-36. Newer QoL scores (e.g. EQ-5D and PROMIS 29) have been validated and are more specific for stroke patients compared to SF-36⁴⁵⁻⁵³, and easier to obtain than the Patzold Rating⁵⁴. No study to date has reported QOL measures or their changes over time in CASH patients observed without surgery. **It would be useful to assess functional outcome and QOL measures at baseline and document their change over time with or without a symptomatic re-bleed.** One or more may be fit for use as a putative outcome in clinical trials of pharmacotherapies, and may even be useful in future surgical trials. As to the QSM and DCEQP biomarkers of lesional hemorrhage and permeability, even if they are successfully and reliably deployed at multiple sites, **it remains unclear how they change during longitudinal follow-up in cases with CASH, and whether their changes are more sensitive than clinical events.** The gaps of knowledge regarding outcome measures in clinical trials are addressed in Specific Aim 3 of this proposal.

Urgent Need for Clinical Trial Readiness. Potential drug development for CASH is very promising, but also illustrates what past-NINDS Director [name] described as “an embarrassment of riches”. As with many rare neurologic diseases, fundamental discoveries have identified cogent mechanistic targets for therapies, but their development into viable clinical solutions invariably meets obstacles and uncertainties in trial readiness. In this disease, there is a huge opportunity through clinical equipoise to target CAs with recent SH, where surgical resection of lesion is not undertaken, with the aim of preventing recurrent bleeding within 2-3 years. There are unique collaborations among major experts and stakeholders in place, yet a critical “Valley of Death” awaits drug development in the absence of readiness for multi-site clinical trials. Obstacles include a lack of harmonization of screening, baseline cohort characterization, prevalence rates and screen/enroll ratios, risk stratification and the assessment of clinical, functional and biomarker outcomes at multiple sites. Further gaps include the unknown rate and sensitivity (fitness for purpose) of outcome parameters during follow-up, needed to postulate treatment effects. These obstacles and gaps are readily addressed by the proposed clinical readiness project. The timing cannot be more opportune, with therapeutic targets identified, and several drugs ready to benefit from a track to clinical testing in about five years.

4.3 END OF STUDY DEFINITION

A participant is considered to have completed the study if he or she has completed all phases of the study including the last visit or the last scheduled procedure shown in the Schedule of Activities (SoA), Section 1.3.

Cases whose CASH lesion has been resected will be considered to have reached endpoint, and will not be followed further during the study. The indication for surgery shall be noted, including any SH prior to CASH lesion resection.

Cases who develop a recurrent SH during follow-up, and their CASH lesion has not been excised, will remain in the study until they complete follow- up, and will undergo all scheduled assessments.

If an enrolled subject decides to discontinue the study, fails follow-up, or develops an exclusion criterion after enrollment in the study (becomes pregnant, undergoes CASH lesion excision, etc.), he/she will be considered an attrition after recording the causative event. Data collected prior to the attrition shall still be included in the study and no further patient follow-up will take place. An allowance in sample size calculation is made for up to 30% attrition or missing data from any cause.

5 Study Population

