1 PROTOCOL SUMMARY

1.1 SYNOPSIS

Title:	Trial Readiness in Cavernous Angiomas with Symptomatic Hemorrhage
Study Description:	This U01 project will address gaps in knowledge and barriers to clinical trial readiness in cerebral cavernous angioma patients with recent symptomatic hemorrhage (CASH)
Objectives:	
Primary Objectives:
 
1. To assess enrollment rates, harmonize data and determine baseline characteristics of patients with CASH across sites2. MRI Biomarker Validations3. Rate of recurrent symptomatic hemorrhage over 2 years in patients with CASH. 
Secondary Objectives: Functional status of CASH cases at enrollment and during follow-up; impact of bleed on functional status

Endpoints:	
Primary Endpoint (Aim 3):
 
• Recurrent bleeding during follow-up, homogeneity in years 1 and 2 
Secondary Endpoints (Aim 3):
 
• Biomarker changes during follow-up, homogeneity in years 1 and 2• Functional status and quality of life change in years 1 and 2 compared to baseline
Study Population:	Adult patients with cerebral cavernous malformations (CCMs) who have had a symptomatic hemorrhage within the prior year, where the bleeding lesion has not been excised or radiated
Phase:	Trial readiness
Description of Sites/Facilities Enrolling Participants:	Seven high volume cavernous angioma clinical centers University of Chicago, Mayo Clinic, University of Utah, University of New Mexico, Barrow Neurological Institute and University of San Francisco and Johns Hopkins University. Additional sites may be added as needed to reach enrollment goals.
Description of Study Intervention:	This is an observational cohort study of CASH cases with no intervention.
Study Duration:	The study will last 5 years.
Participant Duration:	Patients enrolled in the Screening and Clinical Assessment (SCA) arm will have a single, baseline visit. Patients enrolled in the Follow-up and

Biomarker Validation (FUBV) arm will have a baseline visit, along with two yearly follow-up visits, for a total of 3 visits. This is an observational study and all study visits can be completed remotely via telephone and/or telemedicine platforms.

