1.3 SCHEDULE OF ACTIVITIES (SOA)

Procedures	Screening	Enrollment/baseline	1 year (12 months ± 1 month)*	2 year (24 months ± 1 month)*

Type of Visit	In Person/Remote	In Person / Remote	In Person/Remote	In Person/Remote
Informed consent	X			
Demographics	X			
Medical history	X			
Verify clinical and radiographic data		X	X	X
Physical exam		X	X	X
Vital signs		X	X	X
Height		X	X	X
Weight		X	X	X
mRS score assessment		X	X	X

EQ-5D questionnaire		X	X	X
PROMIS29		X	X	X
NIH Stroke Scale		X	X	X
QSM/DCEQP MRI sequences*		X	X	X
MRI standard sequences*		X	X	X

(*) to be performed on subset of cases in the FUBV arm

For this trial, some sites will recruit subjects for the SCA arm only while other sites recruit subjects for the FUBV arm. Subjects who are screened for the FUBV arm and do not qualify, will be screened and offered potential enrollment in the SCA study arm, if applicable.

Subjects enrolled in the SCA arm will have one visit only: the baseline visit. It is anticipated the visit will last less than an hour and include consenting, medical and radiographic history review, a physical, vitals and neurological assessments. The visit information and neurological assessments will be completed via interview with the site coordinator who will enter the data into the electronic case report forms.

Subjects enrolled in the SCA arm will not have a standard MRI done at the baseline visit. Instead, data will be collected from their latest MRI scan, from which the CASH lesion was identified.

Subjects enrolled in FUBV arm will have three study visits: Baseline, Year 1 and Year 2. It is anticipated that each visit will last about 2 hours. The visits will include consenting (Baseline only), medical and radiographic history review, a physical, vitals and neurological assessments. The visit information and neurological assessments will be completed via interview either in person or via telephone with the site coordinator who will enter the data into the electronic case report forms. Subjects will have a standard MRI with additional research sequences. MRI with the additional research sequences will be completed when the participant has a regularly scheduled standard of care appointment. The MRI sequences include T1, T2, SWI/VenBold, and post-contrast scans. The research MRI sequences are QSM and DCEQP sequences. No additional gadolinium is required for the additional research sequences.

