2.2 BACKGROUND

Cavernous Angioma: A Common Lesion, an Uncommon Disease. Cavernous angioma (CA) of the brain is also referred to in the literature as cerebral cavernous malformation (CCM), hemangioma or cavernoma. The lesion consists of clustered, giant, blood-filled capillary spaces (“caverns”), lined by endothelium, and separated by an amorphous matrix lacking mature vessel wall angioarchitecture¹. CA occurs in a sporadic form, manifesting a solitary lesion or a cluster of lesions associated with a venous developmental anomaly². The disease is familial in 20-30% of cases, associated with multiple lesions that develop over time throughout the patient’s brain³. The familial form (OMIM [#116860](#);

<http://omim.org/entry/116860>) exhibits a Mendelian autosomal dominant inheritance due to a heterozygous loss-of-function mutation in one of 3 genes (*CCM1/KRIT1*, *CCM2/Malcavernin*, and *CCM3/PDCD10*)⁴⁻¹⁰. Multiple cavernomas may also develop after cranial irradiation. Magnetic resonance imaging (MRI) is the hallmark diagnostic modality for these lesions, including sequences revealing chronic and acute hemorrhage, and tiny occult lesions. CAs are histologically identical in familial and sporadic cases, and harbor somatic mutations in the same three genes¹¹⁻¹³.

CAs are often detected incidentally, or in association with seizures or non-specific symptoms¹⁴⁻¹⁶. The natural history of such lesions is exceedingly benign, with <0.5% annual risk of clinically significant hemorrhage, and there is consensus about these cases not needing interventions beyond symptom management and surveillance¹⁷. But once a lesion has manifested a symptomatic hemorrhage (SH), its untreated clinical course is quite serious, with a 42% (CI 27-58) rate of recurrent bleeding or focal neurologic deficit within 5 years¹⁷⁻¹⁹. CASH is hence a singular clinical entity, distinguishing lesions with a unique risk profile, impacting a patient's life and meriting clinical intervention. The adjudicated definition of CASH²⁰ requires diagnostic evidence of new lesional bleeding or hemorrhagic growth, in association with directly attributable symptoms.

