5.2 EXCLUSION CRITERIA

- (1) have symptomatic spinal CA's
- (2) have received prior brain irradiation.
- (3) cases where verification of SH with clinical and imaging review cannot be accomplished.
- (4) No prior or planned treatment of the symptomatic lesion (after neurosurgical consultation)

Subjects meeting these eligibility criteria are considered eligible for the SCA arm.

Additional FUBV Arm Exclusion Criteria. To be eligible for Aims 2 and 3, CASH cases enrolled in Aim 1 will be further excluded from FUBV arm inclusion for the following reasons:

- (1) unable to undergo MRI with contrast and/or because of contraindications (e.g. pacemaker, metallic foreign body, pregnancy) or other reasons (severe claustrophobia, too large or too heavy for MRI scanner).
- (2) pregnant or breastfeeding women due to unknown harm to fetus/child from MRI.
- (3) Subject will be unable/unlikely to return for follow-up visit

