7.2 LOST TO FOLLOW-UP

If an enrolled subject decides to discontinue the study, fails follow-up, or develops an exclusion criterion after enrollment in the study (becomes pregnant, undergoes CASH lesion excision, etc.), he/she will be considered an attrition after recording the causative event. Data collected prior to the attrition shall still be included in the study. An allowance in sample size calculation is made for up to 30% attrition or missing data from any cause.

The following actions must be taken if a participant fails to return to the clinic for a required study visit:

- The site will attempt to contact the participant and reschedule the missed visit [within 2 months of the study window] and counsel the participant on the importance of maintaining the assigned visit schedule and ascertain if the participant wishes to and/or should continue in the study.
- Before a participant is deemed lost to follow-up, the investigator or designee will make every effort to regain contact with the participant (where possible, 3 telephone calls and, if necessary, a certified letter to the participant's last known mailing address or local equivalent methods). These contact attempts should be documented in the participant's medical record or study file.
- Should the participant continue to be unreachable, he or she will be considered to have withdrawn from the study with a primary reason of lost to follow-up.

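### Section 4.3 ends all follow-up when a FUBV participant becomes pregnant or develops another MRI or contrast contraindication, although that exclusion concerns only the study scan

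*Combined protocol and SAP*

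**What the plan says.** Section 4.3 provides that if a participant "develops an exclusion criterion after enrollment in the study (becomes pregnant, undergoes CASH lesion excision, etc.), he/she will be considered an attrition" once the causative event is recorded. It continues: "Data collected prior to the attrition shall still be included in the study and no further patient follow-up will take place". Section 7.2 gives the same rule but stops earlier, at "Data collected prior to the attrition shall still be included in the study", and says nothing about ending contact.

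The additional FUBV exclusions in section 5.2 include "pregnant or breastfeeding women due to unknown harm to fetus/child from MRI". They also cover inability to undergo contrast MRI because of implants, metal, claustrophobia or body size. Because section 4.3 refers to exclusion criteria in general and its examples are open-ended, a contraindication such as a new pacemaker falls under it as well.

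On mode of assessment, the synopsis says that "all study visits can be completed remotely via telephone and/or telemedicine platforms". Section 1.3 adds that for FUBV participants "neurological assessments will be completed via interview either in person or via telephone with the site coordinator".

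On the endpoint, section 2.2 states that the adjudicated definition "requires diagnostic evidence of new lesional bleeding or hemorrhagic growth, in association with directly attributable symptoms". The entry criterion in section 5.1 likewise asks for diagnostic studies together with new attributable symptoms. Neither names the study's research or contrast MRI.

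**The concern.** The reason for these exclusions is a reason to leave out a scan. Section 4.3 turns it into a reason to stop recording recurrent SH, which is the Aim 3 primary endpoint, and to stop the functional and quality-of-life measures, which are secondary endpoints.

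The rule also fits poorly with other parts of the plan. Section 2.3 foresees continuing the whole study without the gadolinium permeability biomarker if necessary, and notes that QSM needs no contrast. Yet a single participant who can no longer receive contrast would lose QSM and every other assessment. Pregnancy and breastfeeding can end before the Year 2 visit, whereas the loss under section 4.3 is permanent. Sections 4.3 and 7.2 also leave sites with two versions of what happens next.

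At stake is follow-up time in a cohort that expects only 17 to 34 events. Part of the loss would depend on sex, which section 9.4.2 names as a pre-defined subgroup for all endpoints.

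**Working it through.** **1. Does each outcome need the study MRI?**

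| Outcome | Needs the study MRI? | Basis |
|---|---|---|
| mRS, EQ-5D, PROMIS 29, NIHSS | No; interview, in person or by telephone | Synopsis, 1.3 |
| Recurrent SH | Needs diagnostic evidence plus symptoms; the study MRI is not specified | 2.2, 5.1, 5.2 |
| QSM change | Yes, without contrast | 2.3 |
| Permeability (DCEQP) change | Yes, with contrast | 2.3 |

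The study already relies on imaging done in care. Section 1.3 gives SCA participants no study MRI and takes their data from the latest scan that identified the lesion. Since an SH must be symptomatic, an interview can find candidate events, which can then be verified from imaging done in care where it exists.

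**2. The plan's own figures (section 9.2).**
- Evaluable: 120 × (1 − 0.30) = 84. Patient-years: 84 × 2 = 168.
- Events: 0.10 × 168 = 16.8 and 0.20 × 168 = 33.6, stated as 17–34.
- Detectable difference, two-sample t-test (noncentral t), two-sided 0.05, 80% power: 0.770 SD for 17 against 67 and 0.630 SD for 34 against 50. The plan states 0.63–0.77.

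These reproduce, and the sample size arithmetic is not in dispute.

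**3. Size of the loss.** The documents give no rate of incident pregnancy or MRI contraindication, so the counts below are assumptions, as is one year of remaining follow-up each. The 168 patient-years are already net of the 30% allowance, so the right denominator is the time before attrition, 120 × 2 = 240.
- 3 participants: 3/240 = 1.3%
- 6 participants: 6/240 = 2.5%
- 12 participants: 12/240 = 5%

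**4. What retention could gain at most.** Suppose 12 of the participants otherwise lost (10% of 120) were kept for the full two years. That gives 84 + 12 = 96 evaluable, 192 patient-years and 19–38 events. The exact Poisson 95% interval for x events in T patient-years runs from χ²(0.025; 2x)/(2T) to χ²(0.975; 2x+2)/(2T).

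| | Plan (168 patient-years) | 12 more kept (192 patient-years) |
|---|---|---|
| Interval at 10%/year | 0.059–0.162 (width 0.103) | 0.060–0.155 (width 0.095) |
| Interval at 20%/year | 0.140–0.283 (width 0.143) | 0.140–0.272 (width 0.132) |
| Detectable difference, SD | 0.630–0.770 | 0.591–0.725 |

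As in the plan, each event is treated as one re-bleeding patient. If the 12 regained only one year each, the total would be 168 + 12 = 180 patient-years and 18–36 events.

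**The case against.** **SH needs imaging.** A reader might infer that SH, like function, can be collected by telephone with no MRI at all. The documents do not support that. The definition needs diagnostic evidence, section 5.2 speaks of verification by clinical and imaging review, and section 10.1.6 has a second assessor check SH. An interview alone can record symptoms but cannot confirm an event. Participants who cannot have the study MRI may also have less imaging in care, so keeping them could add time at risk with missed events and lower the estimated rate. This stands, and it shapes the fix.

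**The losses are already budgeted.** Section 4.3 itself says the 30% allowance covers attrition from any cause. A reader might set the lost years against 168 patient-years, or conclude that the power statement fails. Neither follows, because these losses lie within the 36 participants already written off. But the allowance protects the numbers only; it is no reason to create avoidable, non-random missing data.

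**Nothing collected is discarded.** Data before attrition are kept, and the Kaplan-Meier and Cox analyses can use that time. This stands; only later follow-up is lost.

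**FUBV is a joint imaging and follow-up arm.** Analyses that pair biomarker change with SH in the same epoch cannot use participants without scans. This stands for those analyses. It does not apply to the SH rate, time to SH, or change in function and quality of life.

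**Conclusion.** The point holds as a cheap improvement to the design and as an inconsistency between sections 4.3 and 7.2. Ending all follow-up goes beyond the reason for the exclusion: functional and quality-of-life measures need no scanner, and SH needs diagnostic imaging but not the study MRI.

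The size is modest. On assumed counts of 3 to 12 participants losing a year each, 1.3% to 5% of the 240 patient-years before attrition is affected. Even the favourable case of 12 kept for two years improves the detectable difference by only about 0.04 SD (0.770 to 0.725 and 0.630 to 0.591).

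The main benefit is avoiding selective loss. A reader might infer that the whole loss falls on women. That is true for pregnancy and breastfeeding, but not for pacemakers, metal, claustrophobia or body size.

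The conclusion assumes that imaging done in care is available for at least some suspected events. Lesion excision appears in the same sentence of section 4.3 but is a separate case, treated there as reaching endpoint, and is not questioned here.

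**What to change.** Amend sections 4.3 and 7.2 together so that they state one rule:
- When the new exclusion concerns MRI or contrast only, omit the affected study MRI and continue the yearly assessments remotely, with the participant's agreement.
- Count SH only when it is confirmed on diagnostic studies under the existing definition. Record symptomatic events without imaging as unverified.
- Treat the participant as missing for the omitted biomarkers only.
- Report a sensitivity analysis of the SH rate and time to SH that censors these participants at the date the study MRI stopped.
- Leave the handling of lesion excision as it is.

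The cost is a short amendment with IRB review, one or two remote contacts per affected participant at visits already scheduled, and one extra analysis. The downside is possibly less complete SH ascertainment in these participants; the sensitivity analysis shows how far the results depend on including their later follow-up.
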